4.2.1.3 Dose Escalation Mode

Dose escalation is planned to proceed in two steps, with two different increments for the radioactivity escalation. In the first step, in order to minimise the number of subjects receiving subtherapeutic activity, the inter-cohort radioactivity escalation will be performed by increment of 3 GBq (1.5 GBq per administration), up to the first study drug related treatment-emergent AE (TEAE) (Grade 2 or higher, except hair loss) or until a DLT occurs. Afterwards, the maximum increment will be reduced to 2 GBq (1 GBq per cycle) for all subsequent cohorts if dose escalation is allowed. However, even if no Grade 2 or higher AE are observed up to a cumulative activity of 11 GBq, radioactivity will be increased by 2 GBq (1 GBq per cycle).

Table 5 illustrates the escalation plan based on the escalation scheme defined above. However, if DLTs are reported, a statistical Bayesian modelling approach will be implemented to produce a more precise dose-DLT curve to guide the dose selection (see details in Attachment 5, Section 19.5) and predict an activity not exceeding the MTCA/MTSA that could be tested in the next cohort.

Planned radioactivity Cohort 1 Cohort 2 Cohort 3 Cohort 4 Cohort 5 escalation Cumulative 5 GBq 8 GBq 11 GBq 13 GBq 15 GBq 2.5 GBq/C 4 GBq/C 5.5 GBq/C 6.5 GBq/C 7.5 GBq/C Per cycle

Table 5 Cohorts and Radioactivity Escalation Plan

C=cycle; GBq=gigabecquerel.

Once the dose escalation has been completed, the MTCA level may be repeated in a last cohort (see Section 4.2.1.4 for stopping rules and Section 4.2.1.1 for MTCA definition). If the MTCA is not reached and if limiting organ dose levels are not exceeded at the highest planned activity (2×7.5 GBq) and if no individual withdrawal criteria are met, an additional cohort (Cohort 6) with three administrations at the highest single administration level may be added (3×7.5 GBq).

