12.2.5 Safety Evaluation

For the overall study, descriptive statistics will be calculated on the safety parameters. No formal statistical analyses of safety data are planned.

Summaries will be prepared by treatment group and, as needed, by timepoint.

All AEs will be coded according to the latest version of the MedDRA and NCI-CTCAE.

Study drug TEAE summaries will include the overall incidence (by system organ class (SOC) and preferred term (PT)), events by maximum intensity, events by relationship to study drug, events leading to discontinuation of study drug and SAEs.

Physical examination findings, vital signs, ECG 3-lead 24h Holter recordings and clinical laboratory parameters will be summarised descriptively at each timepoint. Actual and change from baseline data will be calculated and summarised where data are available. The investigator's interpretation of 12-lead ECGs will be listed.

Concomitant medications will be coded using the latest version of the World Health Organization (WHO) drug dictionary and will be summarised by treatment group and overall with the number and percentage of subjects receiving concomitant medication by drug class and preferred drug name.

The NCI-CTCAE version 5.0 classification [31] will be used to classify all TEAEs and laboratory abnormalities.

Maximum grade or severity will be tabulated by subject for each MedDRA SOC and PT. Analyses of AEs and SAEs will be performed in two different ways: regardless of the relationship to the study treatment and related to the study treatment. Moreover, all AEs without SAEs and SAEs only will be tabulated.

For haematological and biochemical toxicities, the worst NCI-CTCAE grade by subject and by cycle will be tabulated and listed. For white blood cells, neutrophils, platelets and haemoglobin, with associated Grade 3 or 4 toxicities, nadir and day to nadir will be calculated.

A TEAE is defined as any AE that occurs during the active phase of the study if:

- It was not present prior to receiving the first dose of ¹⁷⁷Lu-3B-227; or
- It was present prior to receiving the first dose of ¹⁷⁷Lu-3B-227 but the intensity increased during the active phase of the study; or
- It was present prior to receiving the first dose of ¹⁷⁷Lu-3B-227, the intensity is the same but the drug relationship became related during the active phase of the study.

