#### **3.2.1.1 Adverse events**

AEs will be coded using the Medical Dictionary for Regulatory Activities (MedDRA) latest version at Ipsen coding department at the time of corresponding database lock and NCI-CTCAE version 5.0 will be used for the grade's classification.

Listings will be presented by treatment group, subject, start date-time, primary system organ class, preferred term and reported term for all AEs recorded during the study, after IMP screening administration, for core trial, additional cycles and follow-up long term separately.

Listings of all AEs, serious adverse events (SAE), AEs leading to withdrawal and listing of deaths will also be presented.

TEAEs will be flagged (\*) in the listing of AEs and will be summarised.

A TEAE for the IMP screening administration is defined as any AE that occurs after the IMP screening administration if:

- It was not present prior to IMP screening administration and it had onset before the first dose of IMP during core trial, or
- It was present prior to receiving the IMP screening administration but the grade increased between IMP screening administration and the first dose of IMP during core trial,
- It was present prior to receiving the IMP screening administration, the grade is the same but the causality changed to "related" between IMP screening administration and the first dose of IMP during core trial.

A TEAE for the core trial period is defined as any AE that occurs during the core trial period of the study if:

- It was not present prior to first dose of IMP during core trial period and it had onset before the EOCT/ED visit, or
- It was present prior to receiving the first dose of IMP during core trial period but the grade increased between first dose of IMP during core trial period and EOCT/ED visit,
- It was present prior to receiving the first dose of IMP during core trial period, the grade is the same but the causality changed to “related” between first dose of IMP during core trial period and EOCT/ED visit.

A TEAE for the additional cycles period is defined as any AE that occurs during the additional cycles period of the study if:

- It was not present prior to EOCT visit and it had onset before the EOAC/ED visit, or
- It was present prior to EOCT visit but the grade increased between EOCT visit and EOAC/ED visit,
- It was present prior to EOCT visit, the grade is the same but the causality changed to “related” between EOCT visit and EOAC/ED visit.

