A TEAE for the long-term follow-up period is defined as any AE that occurs during the long-term follow-up period of the study if:

- It was not present prior to EOCT/ED visit or EOAC/ED visit, or
- It was present prior to EOCT/ED visit or EOAC/ED visit but the grade increased between EOCT/ED visit or EOAC/ED visit and end of study,
- It was present prior to EOCT/ED visit or EOAC/ED visit, the grade is the same but the causality changed to “related” between EOCT/ED visit or EOAC/ED visit and end of study.

In addition, adverse events will be assigned to a specific cycle of treatment for core trial and additional cycles. This assignment will be based on the start date of the adverse event: if the AE start date is on or after the date of treatment X and before the date of treatment X+1 (or if the subject does not receive a treatment X+1 or the treatment X+1 date is missing), then the TEAE will be assigned to Treatment Cycle X.

An overall summary table of all AEs will be presented by treatment group and overall, by cycle (if applicable) and overall, after IMP screening administration, for core trial, additional cycles and follow-up long term separately. In addition, an overall summary table will be presented by pooling cycles from core trial and additional cycles.

TEAEs will be summarised by treatment group and overall with the number and percentage of subjects with AEs classified by primary system organ class and preferred term, by cycle (if applicable) and overall, after IMP screening administration, for core trial, additional cycles and follow-up long term separately. The number of occurrences of a TEAE will also be presented.

In addition, summary tables will also be presented for related TEAEs, SAEs, related SAEs, non-serious TEAEs, TEAEs by decreasing frequency, TEAEs by NCI-CTCAE worst grade (for NCI-CTCAE worst grade  $\geq 3$ ) and TEAEs by most serious causality (category related only).

Summary of TEAEs and related TEAEs will be also summarised by pooling cycles from core trial and additional cycles.

DLTs during cycle 1 or 2 (i.e. occurring between the first administration of Lu-3BP-227 and EOCT/ED) will be summarised by treatment group and overall with the number and percentage of subjects with DLTs classified by primary system organ class and preferred term. The number of occurrences of a DLT will also be presented.

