The number of subjects with at least one DLT or NCI-CTCAE grade  $\geq 2$  (excluding hair loss) will be tabulated by treatment group and overall, by cycle and overall.

Listings of all DLTs will also be presented.

Depending on the number of cases, for all SAEs linked to COVID-19, a summary table will also be provided by treatment group and overall, presenting the number of patients by SOC and PT, by pooling core trial, additional cycles and follow-up long term. Listings of all SAEs linked to COVID-19 will also be presented.

In the event of multiple reports of the same preferred term being reported by the same subject, the NCI-CTCAE worst grade (grade 5 > grade 4 > grade 3 > grade 2 > grade 1) and the most serious causality (related > not related) will be chosen.

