### **5 CHANGES FROM PROTOCOL**

Not applicable.

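### The readable SAP narrows the adverse-event tables that protocol 12.2.5 specifies (a Grade 3 floor, no related-event grade table, no summary of events that stopped study drug) and declares no change

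*SAP*

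**What the plan says.** **Protocol 12.2.5 (Safety Evaluation).** The TEAE summaries are to cover, among other items, "events leading to discontinuation of study drug and SAEs". On grade, the section says "Maximum grade or severity will be tabulated by subject for each MedDRA SOC and PT", and it sets no lower limit. The next sentence has the AE and SAE analyses done in two ways: "regardless of the relationship to the study treatment and related to the study treatment".

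**SAP 3.2.1.1 (Adverse events).** After the main TEAE table by SOC and PT, "summary tables will also be presented for related TEAEs, SAEs, related SAEs, non-serious TEAEs, TEAEs by decreasing frequency, TEAEs by NCI-CTCAE worst grade". A bracket then restricts the worst-grade table to worst grade 3 or above. A further table gives TEAEs by causality, related category only, without grade. For events that ended participation, the SAP plans listings: "AEs leading to withdrawal and listing of deaths will also be presented". DLTs are both tabulated by SOC and PT and listed. A combined count begins "The number of subjects with at least one DLT or NCI-CTCAE grade" and continues with 2 or higher, excluding hair loss; it has no causality condition.

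**SAP section 5 (Changes from protocol).** The whole entry is "Not applicable".

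**The concern.** Establishing safety and tolerability is the primary phase I objective, and the SAP makes the safety population its primary population. The study enrols subjects with advanced cancer, in whom some adverse events will come from the disease. A reader comparing activity levels therefore wants to see how severe the related events were at each level. The planned tables give severity without cause, and only from Grade 3 up, or cause without severity. A reader also wants to know how many subjects stopped study drug because of an event and which events those were. The protocol promised a summary of this, and the readable SAP offers a listing. Because section 5 declares nothing, a reader of the final report would not be told that the output is narrower than the protocol describes.

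**Working it through.** The plan states no figure to reproduce here. The check is a comparison of texts, followed by a short calculation of what the separate tables can and cannot tell a reader.

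**1. Grade.** Protocol 12.2.5 asks for maximum grade by subject, SOC and PT with no floor. SAP 3.2.1.1 tabulates worst grade only where it is 3 or higher, so subjects whose worst grade for a term is 1 or 2 drop out of the table. SAP 3.2.1.2 has a worst-grade table without that floor, but only for haematology and biochemistry and without causality.

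**2. Grade by relationship.** In protocol 12.2.5 the two-way sentence directly follows the maximum-grade sentence. Read together, they call for a maximum-grade table for all events and another for related events. The readable SAP has the first, cut at Grade 3, and not the second.

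**3. Stopping study drug.** Protocol 12.2.5 names this as a TEAE summary. SAP 3.2.1.1 lists AEs leading to withdrawal. SAP 3.2.4 tabulates how many subjects withdrew from the study and why, which is neither a table of AE terms nor the same event as stopping the drug.

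**4. Combined count.** The SAP's count of DLT or Grade 2 and higher, of any cause, follows protocol 12.2.4, so it is not a departure. Protocol 12.2.4 also wants the type of Grade 2 or higher event shown. SAP 3.2.1.1 carries this over for DLTs only.

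**5. What the separate tables leave open.** Take one preferred term in a group of n subjects, with a subjects at Grade 3 or higher (any cause) and b subjects with the event related. The number in both tables lies between max(0, a + b − n) and min(a, b). The counts below are assumed, for illustration only.

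- n = 5, a = 3, b = 3: max(0, 3 + 3 − 5) = 1 to min(3, 3) = 3, that is 20% to 60%.
- n = 3, a = 1, b = 2: max(0, 1 + 2 − 3) = 0 to 1, that is 0% to 33%.
- n = 30, a = 12, b = 18: max(0, 12 + 18 − 30) = 0 to 12, that is 0% to 40%.

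These equal the bounds on related Grade 3 or higher only if each subject has one record of the term. If a subject can have a severe unrelated record and a mild related one, the lower bound is 0 in every case, so the first range widens to 0 to 3.

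The DLT table raises the lower bound somewhat, because DLTs are IMP-related by definition. It does not close the gap: under protocol 4.7.1.1, a related Grade 3 thrombocytopenia without meaningful bleeding, or a related Grade 3 gastrointestinal event that settles within 48 hours, is not in itself a DLT.

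**The case against.** **The protocol lists intensity and relationship as separate summaries, as the SAP does.** The two-way sentence could be met by the TEAE, related TEAE, SAE and related SAE tables. This is a possible reading, and 12.2.5 nowhere names a related Grade 2 or Grade 3 rate. A reader might infer that it requires such rates; it does not. But the position of the two-way sentence favours the crossed table, and the reading does not explain the Grade 3 floor or the missing discontinuation summary.

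**Escalation does not depend on these tables.** This stands. A reader might infer that the missing tables feed the dose decisions. Under protocol 4.2.1.3 the larger increment applies "up to the first study drug related treatment-emergent AE (TEAE) (Grade 2 or higher, except hair loss) or until a DLT occurs", which is a first occurrence and not a rate. The Safety Review Committee and the sponsor decide on data reviewed during the trial, and DLTs are tabulated.

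**The combined Grade 2 count is the protocol's own.** This also stands. It is tempting to call the lack of a causality condition a third SAP departure, because the escalation trigger concerns related events. Protocol 12.2.4 specifies the count in that form, so any mismatch lies between protocol 12.2.4 and 4.2.1.3. Restricting the table would itself depart from 12.2.4; rows can only be added.

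**Listings allow a hand count.** With three to five subjects per cohort and at most 30 treated, this is partly true, although the readable text does not spell out the listing columns. It does not meet a commitment to tabulate.

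**The rule for repeated terms looks hazardous.** SAP 3.2.1.1 takes the worst grade and the most serious causality without requiring that they come from one record. A reader might infer that this corrupts a planned table. No table in the readable text crosses the two, so the hazard arises only when the related-by-grade table is added.

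**Blacked-out text.** The rows of the overall AE summary are not specified and the later SAP appendices are redacted, so absence can be claimed only for what can be read.

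**Conclusion.** The point holds as an undeclared narrowing of protocol-specified safety output in the readable SAP. There are two main shortfalls against protocol 12.2.5: the TEAE worst-grade table is cut at Grade 3 and has no related-event version, and events that stopped study drug are not summarised. A smaller one, against protocol 12.2.4, is that the type of Grade 2 or higher event is not carried over. The related-event version rests on reading two adjacent sentences of 12.2.5 together; the absence of a grade floor and the discontinuation summary are explicit.

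The consequence is for reporting. No estimate, sample size or escalation decision changes. A reader might go further and infer that the all-cause table would mask a dose-toxicity relation by a stated factor. The documents give no background rate of unrelated severe events, so they support no such figure. They support only the weaker statement that the separate tables do not determine how many subjects had related events of a given grade. The point is worth correcting because it concerns the primary objective and costs little.

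**What to change.** In SAP 3.2.1.1:

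- **Worst grade.** Tabulate TEAEs by SOC, PT and worst grade for all grades and by treatment group, once all-cause and once IMP-related. In the related table, take the worst grade among related records only, so that an unrelated grade is never paired with a related causality.
- **Discontinuation.** Add a summary table of TEAEs leading to discontinuation of study drug, alongside the listing.
- **Combined count.** Keep the all-cause count of DLT or Grade 2 and higher as in protocol 12.2.4, and show the event types that section asks for. Add separate rows for study-drug-related TEAEs of Grade 2 or higher (excluding hair loss) and for DLTs, so that the event class in protocol 4.2.1.3 can be read directly.

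If the sponsor prefers the narrower tables, SAP section 5 should say so and give the reason.

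The cost is SAP wording and a few extra tables. Protocol 8.1.2 already has grade and causality recorded for every AE. The sponsor should confirm that the eCRF distinguishes stopping study drug from leaving the study. No dose or clinical rule is affected.

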#### 3.2.1.2 *Laboratory data*

Haematological and biochemistry toxicities will be recorded and graded according to the NCI-CTCAE criteria, version 5.0.

A separate listing of normal ranges for standard international (SI) units will be provided (by age and gender where relevant) for all laboratory data (whenever relevant) as well as a listing of NCI-CTCAE grades with corresponding laboratory ranges.

Laboratory data (haematology, biochemistry, urinalysis and hormones) will be listed in SI units and abnormal values will be flagged (High [H], Low [L], clinically significant [CS], NCI-CTCAE grade [G] (for haematology and biochemistry)) where applicable, for core trial, additional cycles and follow-up long term separately (only core trial for hormones). Any unscheduled laboratory assessments will be flagged [U] in the listings.

In addition, a listing will be presented of all values for a subject with at least a clinically significant abnormal laboratory value.

The baseline will be defined as the last available (and reliable if applicable) assessment collected prior to first IMP administration.

For haematology and biochemistry, summary statistics will be presented by treatment group at each scheduled assessment for actual values and changes from baseline, for core trial, additional cycles and follow-up long term separately.

Shift tables from baseline to each applicable post baseline visit will be presented by treatment group using the number and percentage of subjects with low, normal or high values, for core trial, additional cycles and follow-up long term separately.

The NCI-CTCAE worst grade by subject, by cycle and overall, will be summarised by treatment group, for core trial, additional cycles and follow-up long term separately as well as by pooling cycles from core trial and additional cycles. All non-missing post-baseline values (including unscheduled visits and retest measurements if any) will be used to derive the worst grade.

A listing of NCI–CTCAE grade 3 and 4 toxicities will be produced. For white blood cells, neutrophils, platelets and haemoglobin, with associated Grade 3 or 4 toxicities, nadir and day to nadir will be calculated and listed.

Additionally, a listing of out of range values with parameters that could not be graded using NCI-CTCAE grade will be provided with the H and L flags.

Box plots and scatter plots over time will be provided with all treatment groups on the same graph for the following parameters: haemoglobin, neutrophils, white blood cells, platelet count, ASAT, ALAT, alkaline phosphatase, creatinine, eGRF, total and conjugated bilirubin.

For continuous urinalysis, summary statistics will be presented by treatment group at each scheduled assessment for actual values and changes from baseline.

For categorical urinalysis (negative/trace/positive) frequency tables will be presented at each scheduled assessment by treatment group.

Shift tables from baseline to each applicable post baseline visit will be presented by treatment group using the number and percentage of subjects in each category, for core trial, additional cycles and follow-up long term separately.

For hormones, summary statistics will be presented by treatment group at each scheduled assessment for actual values and changes from baseline, for core trial.

Hormones analysis will be analysed in subjects who do not have substitution or therapy impacting one of the respective pituitary axis (e.g. no cortisol sampling in subjects who receive corticosteroids, no thyroid-stimulating hormone and free thyroxine sampling in subjects who have thyroxine substitution).

#### 3.2.1.3 *Physical examination*

A listing with the date and status of assessment of test will be provided by treatment group, subject and date, for core trial, additional cycles and follow-up long term separately.

#### 3.2.1.4 *Vital signs*

Vital signs (supine systolic and diastolic blood pressures, heart rate, weight, BMI and temperature) will be listed at each assessment by treatment group and subject, for core trial, additional cycles and follow-up long term separately. Any unscheduled vital signs will be flagged [U] in the listing.

The baseline will be defined as the last available (and reliable if applicable) assessment collected prior to first IMP administration.

Summary statistics by treatment group will be presented at each scheduled assessment for actual values and changes from baseline, whatever the position, for core trial, additional cycles and follow-up long term separately.

For interpretation of clinical significance (normal / abnormal, not clinically significant / abnormal, clinically significant / not evaluable), a frequency table will be presented by treatment group at each post-dose assessment, for core trial, additional cycles and follow-up long term separately.

